6.3.4 Safety Endpoints

1. Incidence of post-dural puncture headache (PDPH)
2. Incidence of unintended dural puncture (specific to epidural anesthesia)
3. Incidence of paresthesia during needle insertion (specific to neuraxial anesthesia)
4. Incidence of traumatic tap (results in visible blood aspiration)

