6.4.5 Inclusion Criteria

Subjects will be eligible to participate in the study if **all** of the following conditions exist:

1. Males and females aged 18 years and above, inclusive
2. Subjects scheduled for one of the following procedures:
 - Diagnostic LP (collection of CSF and/or measurement of ICP to diagnose hemorrhage or neurological infection)
 - Therapeutic LP (intrathecal injection of therapeutic agents; drainage of CSF to treat pseudotumor cerebri)

- Planned orthopedic or obstetric procedure, such as labor/induction, cesarean section, hysterectomy, or total hip/knee replacement, with neuraxial anesthesia (injection of anesthetic into spinal and/or epidural space to reduce pain during procedure)
- Epidural blood patch (use of autologous blood to close holes in the dura mater and relieve PDPH)

3. Subjects having a BMI $\leq 42\text{kg/m}^2$

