- VerTouch workflow followed (N/A (control group), marking, introducer placement, needle placement)
- Calculation of number of re-insertions (1 less than insertions)
- Incidence of first-insertion success (1 insertion, any number of redirections)
- Calculation of number of passes (sum of insertions and redirections)
- Incidence of first-pass success (1 pass)
- Calculation of localization, insertion, and procedure times (based on start and end times)
- Incidence of traumatic tap
- Incidence of referral to radiology
- Incidence of conversion from spinal to epidural (neuraxial anesthesia only)
- Incidence of paresthesia (neuraxial anesthesia only)
- Incidence of PDPH
- Intensity of PDPH (mild, moderate, severe)
- Incidence of unintended dural puncture (epidural anesthesia only)
- Subject Discomfort Assessment
- Provider Confidence Assessment
- Adverse Event Assessment
- Upload of data from VerTouch

Post-procedure, the subject will be monitored for adverse events, adverse device effects or other reportable observations to ensure safety, entering relevant data into the eCRF. At the conclusion of the visit, the subject will be released and considered complete. After each procedure, imaging data from VerTouch will be uploaded by the designated observer to a study portal to support investigation of any anomalous finds and/or establishment of a human image database.

7.4.2 Visit 2

Visit 2 must occur at 3 ± 2 days following Visit 1. Phone, or other appropriate follow-ups will be made at Visit 2 to assess the presence and intensity of PDPH in subjects, and assess potential adverse events. At the conclusion of Visit 2, a Subject Study Exit CRF will be completed.

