8.1 Subject Population(s) for Analysis

The study populations are defined as follows:

- Intent-to-treat population (ITT): Consists of all randomized subjects according to their randomized group.
- Per-protocol population (PP): Consists of all subjects who received their randomized treatment, did not have an inclusion or exclusion violation, had a procedure success, and did not have a major protocol deviation.

The primary analysis and all study results will be analyzed using the ITT population. The primary analysis will be repeated using the PP population.

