At the time of treatment, data will be collected on concomitant medication; pain and/or anti-anxiety medication(s) given for the procedure; provider level of training, number of years in practice, experience, and specialty; procedure setting; and type of and reason for neuraxial procedure. The subject will be treated, either with the device or the control. The designated observer will also be responsible for counting needle insertions and redirections. Post treatment, the subject will be monitored for adverse events, adverse device effects or other reportable observations to ensure safety, entering relevant data into the eCRF.

A follow-up visit will be conducted at 3 ± 2 days following treatment. The presence of PDPH and potential adverse events will be assessed in all subjects. At the conclusion of the follow-up visit, a Subject Study Exit CRF will be completed. Adverse events identified in the study will be followed to resolution.

Assessment	Visit 1	Visit 2
------------	---------	---------

Statistical Analysis Plan

Client/Project	IntuiTap/VerTouch
Version and Date	V02 – 22 December 2020

	Screening	Treatment	Post-Treatment	Follow-up
Demographics	X			
Medical History	X			
Physical Exam (Height & Weight)	X			
Inclusion/Exclusion Criteria	X			
Informed Consent	X			
Randomization	X			
Concomitant Medications	X		X	
Procedure Completion		X		
Discomfort Assessment			X	
Provider Satisfaction Assessment			X	
PDPH				X
Adverse Event Assessment			X	X
Adverse Device Effect Assessment			X	X

7 Study Populations

The study populations are defined as follows:

- Intent-to-treat population (ITT): All randomized subjects according to their randomized group.
- Per-protocol population (PP): All subjects who received their randomized treatment, did not have an inclusion or exclusion criteria violation, had a procedure success, and did not have a major protocol deviation.

The primary analysis and all study results will be analyzed using the ITT population. The primary analysis will be repeated using the PP population. Subjects who meet the discontinuation criteria will be discontinued from the study.

8 Statistical Methods

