8.3.6 Safety Endpoints

The following safety related endpoints were identified in the protocol:

- Incidence of post-dural puncture headache (PDPH)
- Incidence of unintended dural puncture (specific to epidural anesthesia)
- Incidence of paresthesia during needle insertion (specific to neuraxial anesthesia)
- Incidence of traumatic tap (results in visible blood aspiration)

These would be analyzed as binary endpoints and compared with likelihood ratio chi-squared tests.

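### The PDPH safety endpoint has no new-onset or at-risk limit, so a headache that a blood-patch subject already had at entry can be counted as an incident event

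*Protocol*

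**What the plan says.** Protocol 6.4.5 admits subjects scheduled for "Epidural blood patch (use of autologous blood to close holes in the dura mater and relieve PDPH". Protocol 2.1 describes the procedure the same way, and no exclusion in 6.4.6 removes subjects with current PDPH.

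Protocol 6.3.4 and SAP 8.3.6 list "Incidence of post-dural puncture headache (PDPH" with no restriction by procedure and no onset rule. The same list does restrict other items, for example "Incidence of unintended dural puncture (specific to epidural anesthesia"; paresthesia is likewise confined to neuraxial anesthesia.

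What is measured is presence. Protocol 7.4.2 has the follow-up contact "assess the presence and intensity of PDPH in subjects", and fixes its timing: "Visit 2 must occur at 3 ± 2 days following Visit 1". SAP section 6 says: "The presence of PDPH and potential adverse events will be assessed in all subjects". Protocol 7.4.1 also lists PDPH incidence and intensity among the post-treatment items at Visit 1. The schedules of events show no PDPH assessment at screening.

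On analysis, protocol 8.1 states: "The primary analysis and all study results will be analyzed using the ITT population". SAP 8.3.6 says of the safety endpoints: "These would be analyzed as binary endpoints and compared with likelihood ratio chi-squared tests". SAP 2.1 counts PDPH among the primary safety endpoints.

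**The concern.** By the protocol's own description, a blood-patch subject arrives with PDPH. If presence is recorded in everyone and compared between arms as a yes/no outcome, a headache that began before randomization and has not yet cleared looks the same in the analysis as one that followed the study needle. The sponsor set at-risk limits for two of the four safety endpoints but not for this one, although some eligible subjects already have the condition.

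At stake are the reported PDPH rates and the between-arm comparison of a named safety endpoint. The rates would include events that the study procedure cannot have produced. A few blood-patch subjects falling unevenly between arms could create or mask a small difference.

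**Working it through.** The plan gives no power or precision figure for PDPH, so there is no sponsor calculation to reproduce. The check has two parts.

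**1. Does any rule stop an entry headache from counting?**

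| Element | What the documents provide |
|---|---|
| Eligibility | Blood patch admitted; current PDPH not excluded (protocol 6.4.5, 6.4.6) |
| Endpoint definition | Incidence, all procedures, no onset condition (protocol 6.3.4, SAP 8.3.6) |
| Measurement | Presence, in all subjects (protocol 7.4.2, SAP 6) |
| Baseline PDPH item | None named; only general medical history (protocol 7.4.1) |
| Population | ITT for all results (protocol 8.1, SAP 7) |
| Analysis | Binary, compared between arms (SAP 8.3.6) |

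No row supplies a new-onset rule, an at-risk set or an adjustment for PDPH at entry.

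**2. How large could the effect be?**

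Inputs from the protocol: 48 subjects per arm, 96 in total (6.4.1); three settings about evenly represented (6.1), so about 32 each; listed PDPH rates of 40% for lumbar puncture (LP) and 0.21-1.5% for neuraxial anesthesia (9.3). Table 1 places blood patch in anesthesiology.

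Assumptions not in the documents: all emergency medicine and neurology subjects (64) have LP; k = 2, 4 or 8 blood-patch subjects replace anesthesiology subjects; a fraction f of 25% to 100% still have the headache when assessed.

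- Per event in one arm: 1/48 = 2.1 points; three events: 3/48 = 6.25 points.
- Expected whole-trial rate without blood-patch subjects: (64 × 0.40 + 32 × 0.015)/96 = 26.08/96 = 27.2%.
- Standard error of one arm's rate at that level: √(0.272 × 0.728/48) = 6.4 points.
- Anesthesiology rate with k blood-patch subjects: [(32 − k) × 0.015 + k × f]/32.
- Whole-trial rate: [64 × 0.40 + (32 − k) × 0.015 + k × f]/96.

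| k | Anesthesiology (n = 32), f = 25% to 100% | Whole trial (N = 96), f = 25% to 100% |
|---|---|---|
| 0 | 1.5% | 27.2% |
| 2 | 3.0% to 7.7% | 27.7% to 29.2% |
| 4 | 4.4% to 13.8% | 28.1% to 31.3% |
| 8 | 7.4% to 26.1% | 29.1% to 35.4% |

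For k = 2 and f = 25%, for example, anesthesiology gives (30 × 0.015 + 2 × 0.25)/32 = 0.95/32 = 3.0%.

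Chance imbalance: protocol 7.3 blocks randomization within setting, not by procedure. If 8 blood-patch subjects fall at random into two arms of 48, a 6-2 or more extreme split in either direction has probability about 27% (hypergeometric). If all 8 are among 32 anesthesiology subjects split 16/16, it is 2 × [C(16,6)C(16,2) + C(16,7)C(16,1) + C(16,8)]/C(32,8) = 2 × 1,156,870/10,518,300 = 22%. With 4 such subjects and arms of 48, a 4-0 split has probability about 12%.

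**The case against.** **The definition may already be implied.** Incidence ordinarily means new cases, PDPH is on the anticipated adverse event list (protocol 9.3), and the adverse event definition (9.1) covers only what arises or gets worse during the study. It is true that neither document states outright that presence at Visit 2 equals incidence. But the 9.1 definition governs adverse events, which are summarized separately and only descriptively (protocol 8.2.4, SAP 8.3.7), and nothing links it to this tested endpoint. The documents also use incidence for first-insertion success and radiology referral, where it means only a proportion.

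**The data allow separation.** A reader might infer that a persisting headache cannot be told from a new one. That goes too far: procedure type is recorded (protocol 7.4.1), so blood-patch subjects can be identified. What is missing is a rule that uses this information.

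**The effect may be negligible.** A reader might set 1/48 beside 0.21-1.5% and conclude that one miscounted headache outweighs the whole expected rate. The documents do not support that for an all-subject endpoint: about two thirds of subjects come from settings where the procedure is LP, listed at 40%. The number of blood-patch subjects could be zero. There is no quota for them, and anesthesiology enrollment is to be split between obstetric and orthopedic cases. Naming blood patch as a subgroup level does not promise any number, because levels with fewer than 8 subjects are dropped. The patch is meant to relieve the headache, so only those still present when assessed matter. All of this stands.

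**No arm is favored.** A reader might also infer systematic bias, or that an old headache is attributed to the assigned method. Neither follows: allocation is randomized, an incidence count assigns no cause, and device relatedness is judged separately (9.1). PDPH is also outside the primary test and the secondary hierarchy.

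**Exclusion has a price.** Dropping blood-patch subjects departs from ITT and could lose a new or worsened headache in someone who did receive a study needle. That is fair, and it is why their status should be reported separately.

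**Conclusion.** The concern holds as a gap in the endpoint definition. Followed as written, the plan permits a PDPH that predates the study procedure to be counted as an incident event.

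The size is uncertain and probably modest for the trial as a whole: 2.1 points per miscounted headache in an arm, and a shift of about 0.5 to 8 points in the overall rate of about 27% over the illustrated range of 2 to 8 blood-patch subjects. It is zero if none are enrolled. In anesthesiology viewed alone the distortion is large relative to the listed rate: two such subjects in 32 would move 1.5% to between 3.0% and 7.7%.

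The comparison is blurred rather than systematically biased, provided that the assigned method does not itself change how often the patch relieves the headache. Chance imbalance remains possible. The figures rest on the protocol's listed rates, an even setting mix, and assumed numbers and persistence of entry headaches.

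The gap is worth closing before data are seen, because SAP 2.1 names PDPH as a primary safety endpoint and the correction needs little.

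**What to change.** In protocol 6.3.4 and SAP 8.3.6:

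- Define the endpoint as PDPH with onset after the study procedure.
- Analyze it in subjects without PDPH at entry, with blood-patch subjects identified from the procedure type already recorded.
- Report the headache status of blood-patch subjects separately by arm, including any worsening.
- State in protocol 8.1 and SAP section 7 that this endpoint is an exception to the rule that all results use ITT.

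The cost is a few sentences in each document, a slightly smaller denominator for one safety endpoint, and the declared departure from ITT. Excluding blood-patch subjects requires no new data. A yes/no item for PDPH at screening would make the at-risk set explicit for every subject, at the cost of one added CRF field.

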6.1 Overview of Study Design

After Informed Consent is obtained, subjects will be randomized 1:1 into two groups via the block randomization method with a list held in each test setting. Standard landmarking techniques will be used in both groups to identify the procedure area. For subjects randomized to the tactile-imaging group (T), VerTouch will be used to identify an interspinous space and to place a marker, introducer, or needle. For subjects randomized to the palpation group (P), the palpation-landmarking method will be used. After marker, introducer, or needle placement, the procedure will continue in the usual manner for subjects in both groups (**Figure 6**).

A designated study observer within each setting will record the time to identify an insertion site; time to place the marker, introducer, or needle; number of insertions, re-directions, and bone contacts (counted until confirmation of spinal canal access

can be assessed); incidence of procedure success; subject's level of discomfort during landmarking; and provider's level of confidence with the identified insertion site. Total procedure time, incidence of traumatic taps, and incidence of referrals to radiology or pain management will be recorded in all settings. In anesthesiology, incidences of paresthesia, unintended dural puncture, and conversion from spinal to epidural anesthesia, will be collected for exploratory analysis, where applicable. Any usability issues or device malfunctions observed during the clinical study will also be documented.

[figure not shown]

Figure 5. Overall Study Design

Although spinal punctures in all clinical settings involve the same localization and insertion processes, there may be variations in setting, subject, and/or provider characteristics. While early VerTouch testing has not evidenced any corresponding variations in device usability and/or outcomes associated with these variations, the study is designed to capture them.

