Accordingly, EM, neurology, and anesthesiology settings will be approximately evenly represented in the study, with at least 24 subjects enrolled in each. To adequately represent patients undergoing obstetric and orthopedic procedures, enrolled anesthesiology subjects will be approximately evenly split between these sub-settings. The PM setting will not be included in the study, as there are limitations, particularly with respect to reimbursement, for ESIs performed with palpation or other non-fluoroscopic techniques. However, PM providers will be represented in IntuiTap's summative usability study, and undergo the same

anesthesiology training as those clinical study investigators specialized in obstetrics and orthopedics.

Additionally, investigators will form a representative sample of typical neuraxial procedure providers, including MDs (residents, fellows, and attendings), PAs, and CRNAs, where applicable. Residents must be in their second post-graduate year and above, having performed at least 5 neuraxial procedures in the past 12 months, and are considered trainees. Apart from their level of training, investigators should have a representative range of relevant experience, indicated by the approximate number of neuraxial procedures they have performed in the past year. To ensure adequate user variability, a single investigator should perform no more than 20% of procedures in his/her setting (corresponding to a minimum of approximately 6 procedures per investigator). Any provider type not included in the study will have been assessed in formative and/or summative human factors testing.

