6.4 Study Population

Subjects admitted to EM, neurology, or anesthesiology settings that require a neuraxial procedure as part of their management or work up, and that meet inclusion and exclusion criteria will be approached by research staff for enrollment in the study. Spinal punctures in these clinical settings involve the same localization and insertion processes, through access to the spinal canal. Written informed consent will be obtained in person by the study coordinator or designee.

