- BMI (kg/m^2): underweight (<18.5), normal (18.5-24.9), overweight (25-29.9), class 1 obesity (30.0-34.9), class 2-3 obesity (≥ 35.0)
- Age (years): adolescent (<22), young adult (22-40), middle-aged adult (41-65), older adult (>65)
- Provider type: MD, PA, CRNA, AA, NP
- Provider specialty: emergency medicine, neurology, anesthesiology
- MD level (MDs only): resident, fellow, attending
- Provider years in practice: <5 , 5-10, >10
- Provider experience (number of neuraxial procedures in past 12 months): 5-25, 26-50, 51-100, >100

- Neuraxial procedure: diagnostic LP, therapeutic LP, neuraxial anesthesia, blood patch
- Medication given for procedure: none, pain, anti-anxiety
- Needle type: spinal 20-22G cutting, spinal 20-22G non-cutting, spinal >22G, Tuohy, CSE
- VerTouch workflow (VerTouch subjects only): marking, introducer placement, needle placement

Subgroup levels will only be considered if there are at least 8 subjects within the covariate level across both treatments.

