8.2.3 Additional Analyses

The tertiary and exploratory endpoints will be summarized descriptively. Tertiary endpoints of localization time, insertion time, and number of bone contacts will also be evaluated for homogeneity of the group results using a Mann-Whitney test. The exploratory endpoint of procedure time will also be evaluated with a Mann-Whitney test. The tertiary, safety, and exploratory incidence endpoints will be evaluated for homogeneity of the rates across the treatment groups using likelihood ratio tests.

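### Paresthesia has a planned between-arm comparison, but its dedicated item and analysis cover neuraxial anesthesia only, so about 64 of 96 subjects (the LP subjects) have no paresthesia-specific item or rate

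*Protocol*

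**What the plan says.** Protocol 6.3.4 lists "Incidence of paresthesia during needle insertion (specific to neuraxial anesthesia" among four safety endpoints. The synopsis and SAP 8.3.6 carry the same limit. The post-treatment data list in Protocol 7.4.1 has the matching item, "Incidence of paresthesia (neuraxial anesthesia only". Protocol 6.1 and SAP 4 restrict by setting instead: "In anesthesiology, incidences of paresthesia, unintended dural puncture, and conversion from spinal to epidural anesthesia, will be collected for exploratory analysis, where applicable".

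Neuraxial anesthesia here does not mean every neuraxial procedure. The covariate list in Protocol 8.2.2 reads "Neuraxial procedure: diagnostic LP, therapeutic LP, neuraxial anesthesia, blood patch". SAP 8.3.3.4 uses the same four levels, and Table 1 in Protocol 3.9 makes the same separation.

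A comparison between arms is planned. Protocol 8.2.3 states: "The tertiary, safety, and exploratory incidence endpoints will be evaluated for homogeneity of the rates across the treatment groups using likelihood ratio tests". SAP 8.3.6 also specifies likelihood ratio chi-squared tests for the safety endpoints.

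On enrollment by setting, Protocol 6.1 says "EM, neurology, and anesthesiology settings will be approximately evenly represented in the study, with at least 24 subjects enrolled in each", within a target of 96 (Protocol 6.4.1).

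**The concern.** The limit on unintended dural puncture follows from the procedure, because an LP enters the dura on purpose. Nothing comparable applies to paresthesia, and neither document gives a reason for its limit. Three parts of the protocol point the other way:

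- Protocol 6.4 says "Spinal punctures in these clinical settings involve the same localization and insertion processes, through access to the spinal canal", and 6.1 makes a similar statement.
- Protocol 9.3 lists paresthesia among the anticipated LP events, at 13%.
- Traumatic tap, another safety endpoint arising from needle insertion, is not limited in this way: "Total procedure time, incidence of traumatic taps, and incidence of referrals to radiology or pain management will be recorded in all settings".

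At stake is coverage. The device is studied in three settings, but the planned paresthesia comparison would describe roughly one third of the subjects. No success criterion depends on it.

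The status of the endpoint also varies. It is a safety endpoint in Protocol 6.3.4 and SAP 8.3.6, a primary safety endpoint in SAP 2.1, and exploratory in Protocol 6.1 and SAP 4. That is an editorial matter and adds nothing to the severity.

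**Working it through.** **Base.** The documents give no sample size or power for paresthesia. The total of 96 does agree with the plan's own calculation: 48 per group, 50% versus 81% first-attempt success, two-sided 0.05, gives 90.4% power against the stated 90%.

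**Subjects outside the endpoint.** Table 1 places LP in emergency medicine and neurology, and neuraxial anesthesia and blood patch in anesthesiology. Assume that every emergency medicine and neurology subject has an LP.

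- Even split: 2 × 96/3 = 64 (67%).
- Fewest: 24 + 24 = 48 (50%).
- Most: 96 − 24 = 72 (75%).
- Blood patches add to these, but the documents give no number. They are clearly outside under Protocol 6.3.4 and 7.4.1 and SAP 8.3.6. They are less clearly outside under Protocol 6.1 and SAP 4, which restrict by setting.

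**Expected LP events at the listed 13%.** 64 × 0.13 = 8.3 (about 4 per arm); 48 × 0.13 = 6.2; 72 × 0.13 = 9.4.

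**What an LP comparison could show.** The half-width of the 95% interval for the difference is 1.96 × √(2 × 0.13 × 0.87 / n per arm). Power is exact, for 13% versus 26% at two-sided 0.05. The Fisher rule means Fisher's exact test when any cell is below 5 (Protocol 8.2, SAP 8.1), and otherwise the likelihood ratio test.

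| LP subjects per arm | Half-width (points) | Power, likelihood ratio | Power, Fisher rule |
|---|---|---|---|
| 24 | 19.0 | 0.215 | 0.135 |
| 32 | 16.5 | 0.260 | 0.182 |
| 36 | 15.5 | 0.299 | 0.233 |

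With 13% in both arms and 32 per arm, at least one cell falls below 5 with probability 0.84, so the Fisher rule would usually apply.

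**Does pooling all 96 sharpen the overall comparison?** Hold LP at 13% with 32 per arm and anesthesia at 16 per arm, and vary the anesthesia rate. The pooled rate is (2 × 13% + anesthesia rate)/3, entered in the same formula with 48 per arm. At 3%, for example, the pooled rate is 29%/3 = 9.67% and the half-width is 1.96 × √(2 × 0.0967 × 0.9033 / 48) = 0.118.

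| Assumed anesthesia rate | Anesthesia only, 16 per arm (points) | All subjects, 48 per arm (points) |
|---|---|---|
| 13% | 23.3 | 13.5 |
| 5% | 15.1 | 12.2 |
| 3% | 11.8 | 11.8 |
| 1% | 6.9 | 11.4 |

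The interval narrows only if the anesthesia rate exceeds about 3%. The documents do not support any such rate.

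**The case against.** The strongest reply is that the events are not lost. Protocol 9.4 and 9.4.1 require every adverse event to be recorded, 7.6 schedules adverse event assessment for every subject after treatment and at Visit 2, and 8.2 promises listings of all CRF data. This stands, so a reader who infers that LP paresthesia would go uncollected is mistaken. It does not close the gap. The planned adverse event tables (Protocol 8.2.4, SAP 8.3.7) give totals and breakdowns by device relationship, seriousness and severity. None of them isolates paresthesia. LP subjects would also have only general adverse event recording where anesthesia subjects have a dedicated item.

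A second reply is that an LP comparison would be weak and the restriction is a consistent design choice. Both are true. The safety endpoints have no stated power in any setting, however, so low power does not explain leaving these subjects out.

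Two stronger readings are tempting and fail:

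- A reader might claim a 42% narrower interval from covering all subjects (1 − √(32/96) = 0.423). That needs one common rate across procedures. As shown above, the absolute interval can also stay the same or widen.
- A reader might set 13% for LP against the 0.018% that Protocol 9.3 gives for neuraxial anesthesia, and conclude that the plan looks only where the event hardly occurs. The protocol describes the first as nerve root irritation and the second as transient neurologic injury. The two may not measure the same thing, so the contrast is not safe.

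**Conclusion.** The point holds as a gap in coverage and reporting. A safety endpoint with a planned between-arm test omits about 64 of 96 subjects (48 to 72), plus any blood patches, from its dedicated item and its analysis. No reason is given, and the protocol itself expects the event in LP.

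The count assumes that LP is done in emergency medicine and neurology only, as Table 1 indicates. The expected 8 events (6 to 9) take the protocol's 13% at face value.

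The benefit of closing the gap is a descriptive LP paresthesia rate by arm. At 13% and 32 per arm the half-width on the difference is about 16 points, and power to detect a doubling is 18% to 26%. Better overall precision is not part of the case. Severity is low: this is a cheap improvement worth considering, and the primary conclusion does not depend on it.

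**What to change.** Remove the neuraxial-anesthesia restriction for paresthesia only, in the protocol synopsis, 6.1, 6.3.4 and 7.4.1 and in SAP 4 and 8.3.6. Leave the restriction on unintended dural puncture as it is.

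Have the existing study observer complete one paresthesia item for every subject, LP and blood patch included, with one written definition and one way of asking. The definition matters because Protocol 9.3 describes the event differently by procedure.

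Report the item by arm within each procedure type and overall, with denominators and 95% intervals. Give the endpoint one status across Protocol 6.1 and 6.3.4 and SAP 2.1, 4 and 8.3.6.

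The cost is one more CRF item for LP and blood-patch subjects, wording edits in six places and the status label in SAP 2.1. No visits or staff are added. If the study has already started, Protocol 13.3 also requires a documented amendment with IRB approval.
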